3.1.2 Reference standard

Page 16 of 53

IDEAL BACKPACS Protocol Final Version 1.1 date 09-Oct-I2024

The primary reference standard will be clinical diagnosis by a rheumatologist reviewing all clinical and diagnostic parameters. Diagnostic confidence will be reported on an 8 point Likert scale as described in Table 2, with scores of 7 or 8 considered as diagnosed with axSpA. Reviewing rheumatologists will not be provided with any results from existing screening tools to inform the presence or absence of axSpA.

The reference standard for the primary analysis will be comprised of a confirmed diagnosis (a score of 7 or 8) versus normal or equivocal (a score from 1 to 6).

Table 2: Pre-defined reference standard for a diagnosis of axSpA

Diagnostic category	Score	Definition
Normal	1	axSpA definitely not present
Normal	2	axSpA not present
Equivocal	3	axSpA probably not present
Equivocal	4	axSpA possibly not present
Equivocal	5	axSpA possibly present
Equivocal	6	axSpA probably present
Diagnosed	7	axSpA present
Diagnosed	8	axSpA definitely present

The ASAS axSpA classification will be a secondary reference standard (Figure 2).

[figure not shown]

Figure 2: ASAS classification criteria for axial spondyloarthritis (axSpA)

3.1.3 Index tests

Index tests are the BACKPACS model (to be developed within this study) in addition to existing referral strategies described in Table 3.

Page 17 of 53 IDEAL BACKPACS Protocol Final Version 1.1 date 09-Oct-l2024

Table 3: Index tests

Index tests	Assessment
The Baraliakos strategy [9]	Assesses 3 clinical variables. If 2 or 3 of these variables are present (or a 'second step' HLA-B27 test is positive) then secondary care referral is suggested:
	 improvement in pain with NSAIDs after 48 hours raised CRP (blood test)
	• early morning stiffness (≥ 30minutes)
	This strategy requires follow up after the initial primary care clinic appointment.
The Modified Braun strategy [45]	Assesses 10 clinical variables and if at least 4 of these 10 variables are present then secondary care referral is suggested:
	 low back pain that started before the age of 35 years waking during the second half of the night because of symptoms buttock pain
	 improvement with movement improvement with non-steroidal anti-inflammatory drugs (NSAIDs)
	 a first-degree relative with spondyloarthritis, current/past arthritis,
	• current/past enthesitis
	current/past psoriasisHLA-B27 genetic test
The 'Assessment of SpondyloArthritis international Society (ASAS) strategy [44]	Patients with chronic backpain (≥ 3 months) with onset before 45 years, should be referred if at least one clinical variable is present:
1	Inflammatory backpain HLA-B27 positive
	 Sacroiliitis on imaging, if available (x-ray or MRI) Peripheral manifestations (arthritis, enthesitis and/or dactylitis)
	 Extra-articular manifestations (psoriasis, inflammatory bowel disease and/or uveitis) Family history for spondyloarthritis
	Good response to NSAIDS Acute elevated phase reactants (c-reactive protein or erythrocyte sedimentation rate)
The CaFaSpA referral strategy[15]	Easy to use and was developed in a primary care setting but was not adopted by NICE spondyloarthritis clinical guideline[3], as the study cohort reported a much lower than expected prevalence of HLA-B27 positive individuals. The explanation for this may be related to the study having a lengthy retrospective recruitment time

Page 18 of 53 IDEAL BACKPACS Protocol Final Version 1.1 date 09-Oct-l2024

for individuals with CBP (median 10 years), whilst
excluding patients diagnosed with axSpA during this
period; many of the excluded individuals with axSpA
would have been HLA-B27 positive. This approach
probably resulted in a substantial reduction in axSpA
prevalence in this cohort, compared to that expected in
real-life clinical practice.

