2.2 Co-primary Objectives

- 1) Externally validate the Baraliakos strategy's predictive performance, including sensitivity, specificity, likelihood ratio, calibration and discrimination in a community-based population in the UK.
- 2) Model an alternative UK-specific axSpA referral strategy using combinations of existing Baraliakos predictors and any additional candidate predictors identified in the IDEAL programme evaluation of existing UK axSpA cohorts with pre-existing ethics.

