4.1.3 Consent and PROMS questionnaires

Informed consent is received from patients using the online eICF. Consenting individuals will be booked for a clinic appointment at their local secondary care research centre clinic and will be sent a REDCap database link to complete an online questionnaire prior to their appointment. Up to 3 reminder emails and / or SMS texts may be sent to participants who have not completed their questionnaire.

The questionnaire will include Patient Reported Outcome Measure (PROM) questionnaires as described in Table 5. The questionnaire will be completed online and take around 25 minutes to complete (on a single occasion). The questionnaire will include demographics, brief questions about inflammatory back pain (IBP) symptoms and clinical features (psoriasis and NSAID response), to allow evaluation of whether patient completed screening might contribute towards being an effective screening strategy.

Table 5 Patient Reported Outcome Measures (PROMs)

Variable	Measure	Score
Spinal Pain	Numerical rating scale	0 (no pain) -10 (worst pain)
Fatigue	Functional Assessment of Chronic Illness Therapy (FACIT)[56]	FACIT
	(and/or) Warwick Axial	WASTEd
	Spondyloarthritis Tiredness and	Fatigue 0-10
	Energy scale (WASTEd) [57]	Energy 0-8

Page 27 of 53
IDEAL BACKPACS Protocol Final Version 1.1 date 09-Oct-2024

Disease activity	Bath Ankylosing Spondylitis Disease Activity Index (BASDAI)	Each question is scored on a scale of 0 -10, 0 indicates none and 10 indicates very severe. For the last question, 0 is 0 hours, 5 is one hour and 10 is two or more hours.
Physical function	Bath Ankylosing Spondylitis Disease Activity Function Index (BASFI) [60]	Each question is scored on a scale of 0-10. 0 indicates easy and 10 indicates impossible.
Fibromyalgia	ACR brief criteria [61]	Widespread pain index (0-19)
Quality of life	Evaluation of ankylosing spondylitis quality of life (EASiQoL)[50]	20 questions across the 4 domains of physical function, disease activity, emotional wellbeing and social participation. Each question is scored 0 (no limitation) to 4 (extreme limitation)
NASS self- referral criteria	Back pain onset before aged 40 Insidious onset (i.e. did you bend over and hurt your back) Duration > 3 months Early morning stiffness > 3 months Improves with movement Does not improve with rest Alternating buttock pain Wakes in second half of the night	Yes/no

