		and Leeds Enthesitis Index (LEI)
		16 sites assessed in total: the greater trochanter, quadriceps tendon insertion into the patella, patellar ligament insertion into the patella and tibial tuberosity, Achilles tendon insertion, plantar fascia insertion, medial and lateral epicondyles, and the supraspinatus insertion. Presence or absence of tenderness; max
		score = 16
Mobility	Bath Ankylosing Spondylitis Metrology Index (BASMI)	Index comprising 5 measures of spinal and hip mobility
Personal history	 a. Onset of chronic back pain symptoms b. Dactylitis c. Enthesitis d. Skin/nail psoriasis, e. Colitis f. Uveitis g. Anterior chest pain 	Self-reported, current and previous
Family history	Presence in first degree or second- degree relatives* of any of the following: a. Skin/nail psoriasis b. Colitis c. Uveitis, d. axSpA, e. Reactive arthritis, f. PsA	Self-reported (yes/no) and number of relatives affected
Response to NSAIDs	Only if NSAID response is not completely clear. At least one week at max tolerated dose. (If NSAID response if not completely clear) for individuals with no contraindications, min 7-day course of full dose NSAIDs (with telephone evaluation of NSAID response from research team at 1 week)	Self-reported (yes/no)

Page 30 of 53 IDEAL BACKPACS Protocol Final Version 1.1 date 09-Oct-2024

Blood tests	Blood tests			
Diagnostic laboratory tests	HLA-B27	Positive testing according to standard laboratory techniques.		
	CRP	C-reactive protein above upper normal limit in the presence of back pain, after exclusion of other causes for elevated CRP concentration.		
Imaging				
x-ray	Conventional SIJ plain x-rays	Modified New York criteria for each SIJ		
MRI	SIJ and whole spine (30 min scan) arranged within 4 weeks** of clinical assessment.	 (i) Description of oedema and structural features (fat metaplasia, erosions, ankylosis) in SIJs – yes/no for each. Interpretation according to ASAS specifications (bone marrow oedema in typical location 'highly suggestive' of axSpA) - yes/no for MRI positivity (ii) Are there unequivocal features of spinal inflammation? (yes/no) (iii) Overall impression across x-ray and MRI – (a) normal (b) equivocal (c) axSpA (d) other 		

^{*}First degree relative includes an individual's parents, siblings and children. Second degree relative includes grandparent, grandchild, half siblings, aunt/uncle and niece/nephew. **where possible, waiting times may vary between sites.

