86. Braun V, Clarke V: Using thematic analysis in psychology. Qualitative Research in Psychology

2006, 3(2):77-101.

- 87. Braun VC, V.: Thematic analysis. Research methods in social sciences: An A-Z of key concepts: Open University Press.; 2021.
- 88. Creswell JW, Miller DL: Determining Validity in Qualitative Inquiry. Theory Into Practice 2000, 39(3):124-130.

Appendices

Appendix 1: Specification of the variables used for the ASAS-Criteria for classification of Axial Spondylarthritis

Clinical Feature of axSpA	Definition
Inflammatory back pain (IBP)	IBP according to experts: 4 out of 5 of the
, , , , , , , , , , , , , , , , , , ,	following parameters present:
	1. Age at onset < 40 years
	2. Insidious onset
	3. Improvement with exercise
	4. No improvement with rest
	5. Pain at night (with improvement upon getting up)
Good response to NSAIDs	24-48 hours after a full dose of a non-steroidal
	anti-inflammatory drug (NSAID) the back pain is
	not present any more or much better.
	(the clinical co-applicants on the PGfAR IDEAL
	grant have concluded that response after one
	week would be more appropriate)
Arthritis	Past or present active synovitis diagnosed by a physician.
Dactylitis	Past or present dactylitis diagnosed by a
	physician.
Enthesitis	Heel enthesitis: past or present spontaneous
	pain or tenderness at examination of the site of
	the insertion of the Achilles tendon or plantar
	fascia at the calcaneus.
	(a broader evaluation of enthesitis is also being
	evaluated for the IDEAL study cohort)
Psoriasis	Past or present psoriasis diagnosed by a
	clinician.
Inflammatory bowel disease (IBD)	Past or present Crohn's disease or ulcerative
	colitis diagnosed by a physician.
Uveitis anterior	Past or present uveitis anterior, confirmed by an
	ophthalmologist.
Family history	Presence in first-degree or second-degree
	relatives of any of the following:
	a. Ankylosing spondylitis
	b. Psoriasis
	c. Uveitis
	d. Reactive arthritis
	e. IBD
HLA-B27	Positive testing according to standard laboratory
	techniques.
Elevated CRP	C-reactive protein above upper normal limit in
	the presence of back pain, after exclusion of
	other causes for elevated CRP concentration.

Page 53 of 53 IDEAL BACKPACS Protocol Final Version 1.1 date 09-Oct-2024

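### The NSAID item of the co-primary Baraliakos rule would be scored on a mixed or unspecified time window, and its 30-minute stiffness item is not mapped to a named variable

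*Protocol*

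**What the plan says.** Section 2.2 makes this co-primary objective 1: "Externally validate the Baraliakos strategy's predictive performance, including sensitivity, specificity, likelihood ratio, calibration and discrimination". Section 3.1.3, Table 3, sets out the rule: referral if at least two of three clinical items are present, or if the second-step HLA-B27 test is positive. The three items are "improvement in pain with NSAIDs after 48 hours", raised CRP, and early morning stiffness of at least 30 minutes.

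The data for these items come from three places.

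- **Table 6 (section 4.1.4), NSAID response.** One self-reported yes/no. The method column reads "Only if NSAID response is not completely clear. At least one week at max tolerated dose", and provides a course of at least seven days "with telephone evaluation of NSAID response from research team at 1 week".
- **Appendix 1, ASAS variable list.** Good NSAID response is defined at 24 to 48 hours. A note then adds that the co-applicants on the "grant have concluded that response after one" week would be more appropriate.
- **Section 4.1.3 and Table 5, participant questionnaire.** There are brief questions on inflammatory back pain symptoms and on NSAID response, with no time window given. The only stiffness item named is "Early morning stiffness > 3 months", in the row for the NASS self-referral criteria. The BASDAI is also collected: "For the last question, 0 is 0 hours, 5 is one hour and 10 is two or more hours".

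**The concern.** External validation means applying a published rule as it was defined and seeing how it performs in a new population. If an item is recorded to a different definition, two things change at once, the population and the test, and the result cannot separate them. A fall below the published 0.91 and 0.67 (Table 1) might reflect UK primary care, or it might reflect the NSAID item being read at a different time in some participants.

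The timing of the decision also matters. Section 5.1 has the SAP agreed before database lock. A SAP can choose cut-offs and derivations, but it cannot recover a 48-hour response that nobody recorded. This therefore has to be settled in data collection.

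**Working it through.** **1. NSAID item, place by place**

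| Place | Who | Window |
|---|---|---|
| Table 3 (rule definition) | everyone | after 48 hours |
| Table 6 (clinic proforma) | response not completely clear | at least one week, call at 1 week |
| Table 6 | response already clear | none stated |
| Section 4.1.3 (questionnaire) | everyone | none stated |
| Appendix 1 (ASAS variable) | everyone | 24 to 48 hours, then a stated preference for one week |

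No row provides for a recorded 48-hour reading. The window that a participant gets depends on how clear his or her previous NSAID experience was.

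**2. Stiffness item**

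Table 3 needs a duration of at least 30 minutes. The NASS item asks about something else, with a 3-month threshold, and belongs to another tool. If the last BASDAI question covers stiffness duration (an assumption) and is linear, with 5 points for 60 minutes, then 30 minutes is 5 × 30/60 = 2.5. A cut there is possible, but the protocol does not say that this question scores the rule or where the cut lies.

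**3. When a changed NSAID answer matters**

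Under two of three, or HLA-B27 positive, the NSAID answer decides the result only for a participant who is HLA-B27 negative and has exactly one of stiffness and raised CRP. Others are classified the same either way.

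**4. The plan's own power figure**

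Inputs from section 5.2: N = 720, prevalence 14%, sensitivity 90% against 79%, specificity 65% against 58%. Cases: 0.14 × 720 ≈ 101; non-cases: 619. With a two-sided 95% Wald interval:

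- sensitivity: 0.11/√(0.90 × 0.10/101) − 1.96 = 1.73, power 95.8%
- specificity: 0.07/√(0.65 × 0.35/619) − 1.96 = 1.69, power 95.5%

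The stated power of over 90% is reproduced on this reading. It does not depend on item wording. The exact test at one-sided 0.025 is stricter and gives 79.2% for sensitivity and 94.3% for specificity.

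**5. How much room there is (size of shift assumed)**

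With 619 non-cases and the exact test at one-sided 0.025, power to exclude 58% is:

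| True specificity | 65% | 64% | 63% | 62% | 60% |
|---|---|---|---|---|---|
| Power | 94% | 86% | 71% | 51% | 16% |

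With sensitivity held at 90%, the positive likelihood ratio goes from 0.90/0.35 = 2.57 to 0.90/0.40 = 2.25 when specificity falls from 65% to 60%. That is still above the NICE value of 2 cited in section 1.2.

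**6. Illustration of a shift (all marginals assumed)**

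Take independent items in non-cases: stiffness 50%, raised CRP 15%, HLA-B27 8%, NSAID-positive a.

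P(at least 2 of 3) = a(0.50 + 0.15 − 2 × 0.075) + 0.075 = 0.50a + 0.075

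Specificity = (1 − 0.50a − 0.075) × 0.92

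- a = 40%: 0.725 × 0.92 = 66.7%
- a = 45%: 0.700 × 0.92 = 64.4%
- a = 55%: 0.650 × 0.92 = 59.8%

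If the later reading raised positives by 15 points in every non-case, specificity would fall by 6.9 points. If that rise held in one third of them (also assumed), a rises by 5 points and specificity falls by 2.3. The documents give neither the size of the subset nor the direction of the change, and no effect on sensitivity has been worked out.

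**The case against.** The strongest reply is that the one-week assessment is conditional. It applies only where the response is unclear, and the questionnaire asks about NSAID response separately. A reader might infer from Table 6 and Appendix 1 that one week replaces 48 hours for everyone, so that the published rule is not validated at all. The documents do not support that. What stands against the plan is narrower: in one subset the item departs from Table 3, and in the rest its window is not stated.

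A reader might also infer that two of the three clinical items have been changed. For stiffness that is not shown. The 3-month item belongs to the NASS tool, the wording of the inflammatory back pain questions is not given, and the BASDAI may yield a 30-minute cut. The gap is an unstated derivation, not demonstrably missing data.

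The conflict should not be extended to the other strategies. Table 3 sets no NSAID window for the modified Braun or ASAS strategies. Appendix 1 covers past arthritis, and the form may already separate first- from second-degree relatives, since Table 6 defines both and counts those affected.

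Finally, the case report form is not shown and may ask more than the protocol lists. That is possible, but the protocol's own definitions would still disagree, and the form should follow a reconciled text.

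**Conclusion.** The point holds for the NSAID item: Table 3, Table 6 and Appendix 1 conflict, and no 48-hour reading is provided for. Followed as written, the plan scores one of three items in a co-primary index rule on a mixed or unspecified window, which weakens the attribution of any difference from 0.91 and 0.67 to the UK setting. The stiffness item is unmapped, which is a lesser defect.

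The size is unknown. The specificity figures above rest on invented marginals, independence and an invented shift, and apply only to the affected subset. They show that a shift of two or three points would matter for the power to exclude 58%, not that one will occur. A reader might take the all-participant illustration to mean that the 7-point gap between 65% and 58% is nearly used up; the conditional wording in Table 6 does not support applying it to everyone.

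This should be fixed, and early, because an unrecorded response may not be recoverable. No view is taken on which NSAID window is clinically right.

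**What to change.** - Reconcile Table 3, Table 6 and Appendix 1, and state which recorded variable and window feeds each Baraliakos item.
- On the questionnaire or case report form, and in the existing one-week call, record NSAID response at 48 hours and at one week as separate answers.
- Score the Baraliakos rule on the 48-hour value, as Table 3 defines it. Use the one-week value only as a BACKPACS candidate or in a sensitivity analysis. Report any other scoring as a modified rule.
- Add an explicit yes/no for morning stiffness of at least 30 minutes, or state the BASDAI cut in advance.
- For the modified Braun comparator, make sure that first-degree relatives and any buttock pain (Table 5 names only the alternating kind) can be identified separately.

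The cost is a few tick-boxes and a minor amendment. The 48-hour answer given at the one-week call relies on short recall. No change to the NSAID course is proposed.

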3.2 Study Management

The roles and responsibilities for each organisation are documented in the Contractual Agreement and the responsibilities of the (Sponsor/CI/NCTU) specifically are detailed in the Delegation of Responsibilities agreement.

Chief Investigator

The Chief Investigator has overall responsibility for the study and shall oversee all study management. The data custodian will be the Chief Investigator.

Sponsor

University of Nottingham will undertake the role of Sponsor as defined by the UK Policy Framework for Health and Social Care Research 2017. Delegated responsibilities will be assigned to the Chief Investigator, participating NHS Trusts and Nottingham Clinical Trials Unit.

Trials Unit

The study is co-ordinated by the Nottingham Clinical Trials Unit (NCTU).

Programme Management Group

The Programme Management Group (PMG) will be responsible for the day-to-day management of the study. Membership includes (but is not limited to) the CI, Trial Manager, Trial Statistician and other members of the NCTU multidisciplinary team as appropriate. The PMG will ensure high quality study conduct, to time and within budget, monitor all aspects of the conduct and progress of the study, ensure that the protocol is adhered to and take appropriate action to safeguard participants and the quality of the study itself. The PMG will also be responsible for ensuring project milestones are achieved. The PMG will meet regularly during the entire course of the study.

Programme Steering Committee

A Programme Steering Committee (PSC) will be established which includes an independent chair, independent and non-independent members and patient representatives. The role of the PSC is to provide oversight of the study. A meeting will take place approximately 6 months then 18 months after the first participant is recruited with all meetings thereafter taking place approximately every six months during the recruitment phase of the study.

PSC members will be asked to sign the IDEAL PSC Charter which will outline their roles and responsibilities. The PSC will consider and act, as appropriate in accordance with the PSC Charter, and ultimately carries the responsibility for deciding whether the study needs to be stopped on the grounds of safety or efficacy.

Data Monitoring Committee

There will be no separate Data Monitoring Committee (DMC) formed for this project as no safety data is being collected. The PSC will act in accordance with the PSC charter and

Page 19 of 53

IDEAL BACKPACS Protocol Final Version 1.1 date 09-Oct-l2024

oversee the project as appropriate. If the need arises, the independent members of the PSC will have the opportunity perform the role of a DMC (for example, to review confidential data separately to the PMG).

3.3 Duration of the study and Participant involvement

3.3.1 Study Duration

The study is planned to start in October 2024 with recruitment of participants for 15 months and data lock after 22 months.

Participant Duration: It is envisaged that a clinical diagnostic decision would be reached within 6 months of the participant entering the study (and frequently a shorter period of time).

3.3.2 End of the Study

This protocol relates to BACKPACS, which is work package 2 (WP2) of the IDEAL programme grant. The end of this study (WP2) will be the date of final database lock (when we reach a minimum of 720 participants), at which point the final analysis will be undertaken. NCTU will notify the REC when the IDEAL WP2 has ended, and a summary of the clinical study report will be provided within 12 months of the end of WP2. The remainder of the programme grant (WP 3 and 4) will continue and be covered by a separate protocol.

